3.2 Study Endpoints

- Primary Efficacy Endpoint: Acute procedure success defined as the ability to successfully ablate AF sources identified by the Ablamap Software.
- Secondary Efficacy Endpoint: Freedom from documented episodes of AF recurrence following the blanking period (90 days post ablation) through 12 months.

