3.6 Statistical Analysis

The primary efficacy endpoint of this registry is the successful elimination of significant sources of excitation. Target parameter is the activity of the leading source. According to the retrospective data analyzed previously, the critical threshold for significance of a source is an activity of 26%.

Significance of the leading source will be tested in each patient at multiple times, in every procedure performed, in both atria, before and after PVI or PV touch-up and before and after ablation. The effect of targeted ablation will be statistically analyzed by determining the rate of reduction of leading source activity below threshold upon ablation. If an ablation is not successfully reducing the activity or if the location of the leading source changes upon ablation, ablation will be repeated.

The secondary endpoint of the study is freedom from documented episodes of AF recurrence following the blanking period (90 days post ablation) through 12 months.

We will analyze the level of significance of this difference based on the patients with sources above threshold that were successfully ablated and remained AF free versus those patients where no sources or sources below threshold were seen but were not ablated.

Descriptive summary statistics for continuous variables will include the number of subjects, mean, standard deviation or standard error, median, minimum, and maximum. Nominal categorical variables will be summarized using counts and percentages. Ordinal variables may be analyzed as if they were continuously scaled. Subject disposition, the number and percentage of subjects who complete and discontinue as well as reasons for early discontinuation will be presented. Demographic and baseline characteristics will be summarized descriptively.

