5.5 EGF Procedure

The procedure should begin by verifying the effectiveness and durability of the prior PVI for redo subjects or a complete PVI for de novo subjects. Adenosine or isoproterenol may be administered following the PVI to detect dormant reconnections. If pharmacologic challenge is not used to detect dormant reconnections, a 20-minute wait following the last RF application for PVI should be performed. A commercially available, 64-electrode basket catheter will be introduced into both the right and left atria and unipolar electrograms from the basket catheter will be recorded for one minute each. Recordings are then analyzed with the Ablamap Software. If no sources are seen, or only sources below threshold are detected, the basket should be repositioned until the physician is confident adequate endocardial anatomical coverage has been achieved. If sources above threshold

[figure not shown]
are seen, the patient proceeds to ablation. For those subjects that have no identifiable sources or sources below threshold, the investigator may choose to ablate those subjects per their standard ablation practices.

Once the baseline (i.e., post PVI/PVI touch up) EGF maps are complete, the targeted AF source ablations will be determined according to the results of the EGF analysis using a pre-specified threshold. Ablations should be performed using standard, commercially available ablation catheters/systems. 3D-electroanatomical mapping of both atria will be performed using standard, commercially available mapping systems.

High density bi-atrial voltage mapping using a commercially available multipolar diagnostic mapping catheter during the ablation procedure is required and will be collected for analysis.

EGF mapping should be repeated in the RA and the LA until no further EGF sources above threshold are identified. If AF persists after completion of ablations, cardioversion should be performed.

Figure 2. Workflow for portion of procedure involving EGF-Guided ablation following pulmonary vein isolation

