5.9 Subjects Lost to Follow-Up

The investigator will attempt to contact a subject at least three times prior to designating them as lost-to-follow-up subjects; two of these attempts should include attempting to contact subject via registered mail. The investigator will document the date and type of attempted communication and will complete the Study Exit/Completion Form when a subject is confirmed lost to follow-up.

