6.4 Protocol Amendments

If a protocol revision is necessary which affects the rights, safety or welfare of the subject or scientific integrity of the data, an amendment is required. Any modifications to the Clinical Protocol shall be agreed and signed by the investigator(s). The amendment should be submitted to their respective EC/IRB that originally approved the investigation. A summary explaining the changes, the rationale for changes and other documents will be provided in accordance with applicable requirements, to ECs/IRBs and regulatory authorities. Appropriate approvals of the revised protocol must be obtained prior to implementation.

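### The secondary comparison in section 3.6, read literally, makes AF freedom an entry condition for the source-ablated group, so that group is 100% AF-free whatever the data show

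*Combined protocol and SAP*

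**What the plan says.** Section 3.2 gives the secondary efficacy endpoint as "Freedom from documented episodes of AF recurrence following the blanking period (90 days post ablation) through 12 months", and section 3.6 repeats it. The next sentence of 3.6 announces a significance analysis of a difference, based on "patients with sources above threshold that were successfully ablated and remained AF free versus those patients where no sources or sources below threshold were seen". It ends by adding that the second group was not ablated. The difference is not specified in any earlier sentence, and no test, significance level or effect measure is named. The rest of 3.6 on this endpoint is general descriptive statistics.

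Section 5.5 describes how patients reach these groups. Treatment decisions follow "Once the baseline (i.e., post PVI/PVI touch up) EGF maps are complete". For source-positive patients, "EGF mapping should be repeated in the RA and the LA until no further EGF sources above threshold are identified". For patients with no source, or only sources below threshold, "the investigator may choose to ablate those subjects per their standard ablation practices".

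**The concern.** The condition of having stayed AF-free is attached to one group only, and it is the outcome being compared. Source-ablated patients whose AF recurs drop out of the comparison, while patients with recurrence in the other group stay in. A test on groups formed this way says nothing about AF freedom.

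A milder reading takes AF freedom as the numerator, with all successfully ablated source-positive patients as the denominator. That removes the selection on outcome. It still omits source-positive patients whose source was not eliminated, who may do worse. On the natural reading of the closing condition, it also omits source-negative patients whom the investigator chose to ablate, so the comparator depends on an investigator decision.

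This is the only significance test of the clinical outcome in the plan. The planned counts and percentages for the endpoint itself are not affected.

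**Working it through.** **Step 1: logic, no assumptions.** If membership of group A requires AF-free = 1, then P(AF-free | A) = 1 whenever A is non-empty. If true freedom is p in everyone, group B is expected to show p. The expected apparent difference is therefore 1 − p:

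- p = 51%: 49 points
- p = 60%: 40 points
- p = 81.6%: 18.4 points

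These rates come from the Introduction: 51–60% at 12 months for persistent AF and 81.6% for paroxysmal AF. I add 70% as an intermediate value.

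**Step 2: worked case.** The plan gives no figure to reproduce for this comparison. It states only a ceiling of 100 subjects (section 3.3). Assumed here: N = 100, true freedom 60% in everyone, 60 source-positive, 90% eliminated (60 × 0.9 = 54), 75% of the 40 source-negatives not ablated (30), two-sided Fisher exact test at 5%. Expected AF-free counts, rounded: 54 × 0.6 ≈ 32; 30 × 0.6 = 18; 60 × 0.6 = 36; 40 × 0.6 = 24.

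| Reading | Source-positive | Source-negative | p |
|---|---|---|---|
| Literal | 32/32 | 18/30 | 0.00004 |
| AF-free as numerator only | 32/54 | 18/30 | 1.0 |
| All subjects by baseline source status | 36/60 | 24/40 | 1.0 |

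**Step 3: false-positive rate with equal true freedom.** This is an exact enumeration over two binomials, a ~ Bin(n_A, p) and b ~ Bin(n_B, p). It sums the probability of every (a, b) for which Fisher gives p < 0.05. The table tested is [a, 0; b, n_B − b] on the literal reading and [a, n_A − a; b, n_B − b] on the numerator reading.

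| True freedom | Literal, base grid | Literal, wider splits |
|---|---|---|
| 51% | about 100% | 77–100% |
| 60% | about 100% | 65–100% |
| 70% | 98–99% | 43–99% |
| 81.6% | 76–83% | 12–83% |

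- Base grid: 40 or 60 source-positive, 90% eliminated, 75% of source-negatives not ablated.
- Wider splits: 20–60 source-positive, 25–75% not ablated, 90% eliminated.
- If elimination also varies from 70% to 100%, the lowest value is 2%, at 81.6% freedom with few source-positive subjects.
- Numerator reading: 2–5% throughout.
- Groups defined by baseline source status (20, 40 or 60 source-positive): 3–4%.

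**Step 4: subjects left out.** The number in neither group is N − n_A − n_B, where the literal n_A counts only AF-free patients. In the worked case the literal rule omits 100 − 32 − 30 = 38 and the numerator reading 100 − 54 − 30 = 16. Over the full grid, 21–73 of 100 are omitted on the literal reading and 10–66 on the numerator reading.

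**Step 5: residual bias on the numerator reading.** Inflation of the source-positive rate = share with a residual source × gap in freedom between eliminated and residual. With an assumed residual share of 5–10% and a gap of 10–30 points, this runs from 0.05 × 10 = 0.5 to 0.10 × 30 = 3 points. It could be near zero, because mapping is repeated until no source above threshold remains.

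**The case against.** The best defence is that this is loose drafting. A group fixed at 100% leaves nothing to test, so the authors probably meant AF freedom as the thing counted, and on that reading the test keeps its size. That may well be the intention, but the sentence does not say so and no other section settles it. The two readings give p=0.00004 and p=1.0 on the same patients, and the choice could be made after the data are seen.

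A second objection is that the closing condition is also open to different readings. Section 5.5 calls for complete PVI in de novo subjects, so taken strictly hardly any of them count as not ablated, and the comparator could be very small. This stands as a limit on the size: with 54 eliminated and 60% freedom, the literal false-positive rate falls to 66% with 5 comparators and 35% with 3. Both are still far above 5%, and the point is a further reason to rewrite the sentence.

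It is also fair that nearly all the inputs are assumed, that the bias on the numerator reading is small, and that bounds for missing 12-month data go beyond the defect itself. This is a non-randomised registry with no stated power, so the test carries less weight than in a confirmatory trial. None of this makes the written comparison valid.

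**Conclusion.** The concern holds, and the sentence must be fixed. The firm result needs no assumption: on the literal reading the source-ablated group is 100% AF-free for any data, so the comparison is invalid. How often it would mislead depends on assumed group sizes, test and significance level. The false-positive rate is near-certain in most plausible splits at 51–70% freedom, lower at 81.6%, and as low as 2% in one corner. On the numerator reading the test keeps its size. The remaining problems there are the omitted subjects and an inflation of perhaps 0–3 points. Confidence that the wording is defective is high; which reading the authors intended cannot be told from the document.

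**What to change.** Replace the sentence in section 3.6 with a definition along these lines:

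- **Groups:** source status on the completed baseline (post PVI or touch-up) EGF maps of the index procedure, after any basket repositioning. One group has at least one source above the protocol's 26% threshold in either atrium; the other has none. Naming the index procedure matters because section 3.5 allows repeat EGF-guided procedures.
- **Population:** every mapped subject, whatever the ablation result and whether or not extra ablation was given.
- **Outcome:** AF freedom from day 90 through 12 months, used only as the outcome.
- **Report:** the difference with a 95% confidence interval, naming the method. At 36/60 versus 24/40 the Newcombe interval is −18.6 to +19.2 points.
- **Labelled descriptive splits:** source-positive subjects by eliminated versus residual source; source-negative subjects by whether extra ablation was given.
- **Interpretation:** state that the contrast is non-randomised and shows an association with source status, not the effect of EGF-guided ablation.

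As a useful addition, report how many in each group lack a 12-month evaluation (section 5.9 already has sites complete an exit form for subjects lost to follow-up). Show the result with them counted as recurrent and as AF-free. With 10% missing and 60% observed, the range is 0.6 × 0.9 = 54% to 54% + 10% = 64%.

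The cost is a wording change. It may need an amendment, since section 6.4 says that where a revision affects the "scientific integrity of the data, an amendment is required"; that means investigator signature and EC/IRB submission. No new data are needed. The reported contrast will be less favourable than under the literal rule; against the numerator reading the change may be small.

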1. INTRODUCTION

[figure not shown]
Atrial fibrillation (AF) is the most common cardiac arrhythmia and is associated with increased mortality, morbidity and impaired quality of life. Catheter ablation has become the standard of care for symptomatic patients with drug-refractory AF and the cornerstone of ablation remains the electrical isolation of the pulmonary veins (pulmonary vein isolation = PVI).¹ For patients with paroxysmal AF, long-term effectiveness of an approach based on PVI as the sole ablation strategy is reported to be 81.6% at 12 months, 73.8% at 24 months, and 68.1% at 36 months post-ablation.² However, the success rate of PVI for patients with persistent AF is significantly lower with rates of freedom from AF at 12 months post-ablation ranging from 51 up to 60% regardless of the catheter ablation strategy, addition of antiarrhythmic drugs, use of cryoballoon v. RF ablation, or lesion set performed.³⁻⁶ This ceiling of efficacy in the persistent AF population may be attributable to the complex functional mechanisms of AF contributing to an individual patient's disease state.

Beyond the pulmonary vein triggers, the development and persistence of AF depends upon a localized source—a trigger or driver as well as susceptible substrate, such as re-entrant circuits and or regions of fibrotic atrial myocardium with abnormal conduction properties.^{1,7,8} After pulmonary vein isolation has been performed, accurate, enhanced mapping techniques that can localize extra-PV drivers/triggers is needed to further guide the next step in the ablation strategy.

Efforts to hone in on AF mechanisms underlying persistent AF have multiplied and several different methods for identifying these localized sources have been put forth using global or panoramic mapping techniques.⁹⁻¹² However, due to the chaotic nature of the intracardiac electrograms (EGMs) characteristic of AF, identifying active focal sources relevant to the initiation and maintenance of AF has remained challenging.

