4 SUBJECT SELECTION

4.1 Patient Selection-Criteria for Eligibility

Subjects enrolled in the AF-FLOW Registry should be selected from the investigators' general patient population with a history of atrial fibrillation that meet eligibility criteria. Patient selection may also be performed by review of the medical records of those subjects who have had prior AF treatment with ablation therapy. Investigators are responsible for screening all potential subjects and selecting those who meet the eligibility criteria for the study.

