4.2 Study Inclusion Criteria

Subjects must meet ALL the following criteria:

1. Suitable candidate for intra-cardiac mapping and ablation of arrhythmias.
2. Above eighteen (18) years of age or of legal age to give informed consent specific to state and national law.
3. History of documented symptomatic atrial fibrillation.

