5.2 Baseline Data

Subject source data will be collected per the relevant worksheets, medical reports, procedural reports, lab reports and any other original document in the study subject's chart. In case of electronic source data, accessible without audit trail, printouts have to be produced, verified, and confirmed. Source data will be transferred to CRFs.

After eligible subjects have signed an informed consent form and before the scheduled interventional procedure, subjects will undergo a baseline evaluation. This evaluation may be conducted in accordance with the hospital's standard of care procedures.

The evaluation will include but not limited to the following:

- Medical History and Physical Exam:
 - Subject Demographics
 - Baseline Physical Assessment
 - Height and weight
 - Resting blood pressure
 - Resting heart rate
 - Medical History

- History and documentation of AF
- NYHA score
- CHA₂DS₂-VASc score
- Cardiovascular or other medical history as it pertains to eligibility criteria
- Smoking history
- Medication History
 - Class I-IV AAD history, current doses and/or failure or intolerance
 - Other: Anticoagulants and other cardiac medications
- Baseline Imaging
 - Baseline imaging to rule out LA/LAA thrombus may be done at time of procedure or up to 48 hours prior to the start of any study procedure; however, if any evidence of left atrial thrombus is discovered, the ablation procedure will not be performed at that time. The subject may either be excluded from the study or maintained on oral anticoagulation for an additional period of time (at investigator's discretion). Repeat imaging to rule out thrombi will be required prior to study procedure.
 - A new echocardiogram (transthoracic or transesophageal) should be performed prior to ablation procedure if one has not been performed within six months of the enrollment procedure or if previous data is not available.

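### The 12-month comparison in section 3.6 sets non-randomised map-result groups against each other with no adjustment for AF type or de novo/redo status, so case mix can bias it by an amount the documents do not fix

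*Combined protocol and SAP*

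**What the plan says.** Eligibility is broad. Section 4.2 asks for "History of documented symptomatic atrial fibrillation" and does not restrict AF type; section 4.3 excludes nobody for AF type or prior ablation. Section 4.1 allows selection by "review of the medical records of those subjects who have had prior AF treatment with ablation therapy". Section 5.5 gives the two kinds of subject different index treatment: the procedure starts by "verifying the effectiveness and durability of the prior PVI for redo subjects or a complete PVI for de novo subjects".

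Section 3.6 then plans to test the significance of the 12-month difference for "patients with sources above threshold that were successfully ablated and remained AF free versus those patients where no sources or sources below threshold were seen". The sentence ends by describing the second group as not ablated. The section names no stratum, covariate or subgroup; baseline characteristics are only to be summarised descriptively. It does not use the word pooled, but pooling is the default when nothing else is specified.

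The Introduction gives 12-month figures by AF type. For paroxysmal AF with PVI alone, effectiveness is "reported to be 81.6% at 12 months". For persistent AF it cites "rates of freedom from AF at 12 months post-ablation ranging from 51 up to 60" percent, whatever the ablation strategy. Section 5.2 collects "History and documentation of AF" at baseline but does not name AF type as an item.

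**The concern.** The two groups are formed by what the EGF map shows and what was then ablated, so nothing in the design balances them on prognosis. If subjects with above-threshold sources have persistent AF more often than those without, their 12-month AF freedom would be expected to be lower whatever EGF-guided ablation does. That could hide a benefit or make the source-ablated group look worse. An imbalance the other way would flatter it.

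Treatment received may differ as well. A de novo subject has a full PVI on the day. A redo subject with durable isolation and no above-threshold source may have no ablation, because section 5.5 leaves further ablation to the investigator. The objective in section 3.1 is to evaluate whether EGF can guide ablation, and an unadjusted test cannot separate that effect from who falls into each group.

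**Working it through.** The documents give no alpha, power, effect size or sample-size derivation, so there is no design figure to reproduce.

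**Inputs from the documents.** Paroxysmal AF 81.6%; persistent AF 51% to 60% (Introduction); at most 100 subjects (section 3.3).

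**Assumptions.** The share of persistent AF in each group; two-sided 0.05; 50 subjects per group; outcome depends on AF type only, with no effect of EGF-guided ablation. The comparison is taken to be one of rates, which section 3.6 does not achieve as worded (see the objection).

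**Gap between AF types.** 81.6 − 60 = 21.6 points; 81.6 − 51 = 30.6 points.

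**Bias.** Bias = (difference in share of persistent AF) × (gap).

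- 60% against 40%: 0.2 × 21.6 = 4.3; 0.2 × 30.6 = 6.1 points.
- 70% against 30%: 0.4 × 21.6 = 8.6; 0.4 × 30.6 = 12.2 points.

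**Chance of a significant result with no group effect.** For group rates p1 and p2, d = p2 − p1, n = 50 per group and p̄ their mean: s0 = √(p̄(1 − p̄)·2/n), s1 = √((p1(1 − p1) + p2(1 − p2))/n), and the chance is Φ((d − 1.96·s0)/s1) + Φ((−d − 1.96·s0)/s1). Example, 70/30 with persistent AF at 51%: p1 = 0.7 × 51 + 0.3 × 81.6 = 60.2%; p2 = 0.3 × 51 + 0.7 × 81.6 = 72.4%; chance 25.2%.

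| Share persistent, one group vs the other | Bias, points | Chance of p < 0.05 (nominal 5%) |
|---|---|---|
| 60% vs 40% | 4.3 to 6.1 | 7.6% to 9.9% |
| 70% vs 30% | 8.6 to 12.2 | 15.7% to 25.2% |
| 80% vs 20% | 13.0 to 18.4 | 29.5% to 49.3% |
| 100% vs 0% | 21.6 to 30.6 | 66.6% to 91.1% |

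With groups of 70 and 30 instead of 50 and 50, in either order, the 70% vs 30% row becomes 12.7% to 23.4%.

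**Masking.** A true 10-point advantage is cancelled by an imbalance of 10/30.6 = 33 to 10/21.6 = 46 percentage points in the share of persistent AF.

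**How much imbalance mimics significance.** With AF freedom near 70%, an observed difference of 1.96 × √(0.7 × 0.3 × 2/50) = 18 points is just significant. Mix alone reaches that at 18/30.6 = 59 to 18/21.6 = 83 percentage points of imbalance.

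**De novo/redo.** The documents give no outcome rates by this factor, so no size can be calculated.

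**The case against.** Broad entry is deliberate in a real-world registry, and that stands: nothing here argues for narrower eligibility. It does not excuse an unadjusted significance test between self-formed groups.

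The strongest objection is that the calculation does not describe section 3.6 as literally written. Membership of the first group requires having stayed AF free, so its rate is 100% by definition. This stands. It is a prior defect that adjustment would not cure, and the fix has to start there. The second group is also described as not ablated, so the sentence builds in a treatment contrast and leaves unclear where de novo subjects, who all receive PVI, belong.

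Several stronger readings are tempting, and the documents do not support them:

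- **That the bias is 22 to 31 points.** That is the gap between AF types, reached as bias only if the groups separate completely by type. The cited rates also differ in source, measure and ablation strategy, so part of the gap may be definitional.
- **That source-positive subjects will mostly have persistent AF.** The Introduction links localised sources to the development and persistence of AF in general, and is tentative about why results in persistent AF reach a ceiling. It gives no source prevalence by type.
- **That a spurious significant result is likely.** At 70/30 the chance is raised to 15.7% to 25.2%, but most such studies would still not show one.
- **That the primary endpoint has the same problem.** It rests on source activity before and after ablation, and no case-mix bias is shown for it.
- **That the registry rate will be set against the Introduction's rates.** No section plans this.

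**Conclusion.** The concern holds for the secondary comparison only. Section 3.6 tests a difference between non-randomised groups with no stratification or adjustment, in a population open to all AF types and to both de novo and redo subjects. On the protocol's own approximate figures, bias from AF type is 21.6 to 30.6 points times the imbalance in persistent AF: 4.3 to 6.1 points if the shares are 60% and 40%, and 8.6 to 12.2 points if they are 70% and 30%. Those shares are assumptions, and the direction depends on which group holds more persistent AF. The de novo/redo part rests only on the different index treatment in section 5.5.

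**What to change.** In section 3.6:

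1. Define the secondary comparison as AF-freedom rates in groups set by the map and ablation result. Remove the condition of having stayed AF free from the definition of the first group, and state whether PVI counts as ablation when subjects are assigned to the second.
2. Adjust or stratify that comparison for AF type and de novo/redo status.
3. Report the secondary endpoint descriptively by each factor separately, not by their cross-classification.

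In section 5.2, record AF type explicitly under the AF history. Take de novo/redo status from the procedure record.

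The cost is a wording change, possibly one CRF field, and less precise estimates; no new visits, tests or subjects. One factor by map group averages 100/4 = 25 subjects per cell, about ±1.96 × √(0.7 × 0.3/25) = ±18 points at an assumed 70% AF freedom. Crossing both factors would average 100/8 = 12.5, about ±25 points, which is why step 3 keeps them separate. The comparison remains observational, and other differences between the groups would be untouched.
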